2.5 Regulatory

This study will be conducted in compliance with the protocol approved by the Institutional Review Board, and according to Good Clinical Practice standards. No deviation from the protocol will be implemented without the prior review and approval of the IRB except where it may be necessary to eliminate an immediate hazard to a research subject. In such case, the deviation will be reported to the IRB as soon as possible.

3. Objectives and Endpoints

Objectives	Endpoints
Primary	
1.To understand the treatment effects of Topiramate for sudden sensorineural hearing loss	1.Pure tone audiology improvement (day 0 and day 84)
Secondary	
1.To understand the additional treatment effects of topiramate for sudden hearing loss events	1. word recognition score improvement (compare day 0 and day 84) 2. The improvement rate and gain of pure tone audiology (compare day 0 and day 56)

4. Study Design

4.1 Overall Design

This is a clinical study using medication approved and currently prescribed in the clinic. The included patients were those who came to clinic and was diagnosed as SSNHL within 14 days of

Protocol: The role of migraine prophylaxis agent topiramate in treating patients with migraine and sudden

sensorineural hearing loss

Version: 6

Date: 20220812

onset. Those patients were asked whether they agreed to participate this clinical trial. Patients who were diagnosed as SSNHL but was later found to be other disease such as Meniere's disease, CP angle tumor will be excluded from this study.

The involved patients were randomized divided into two groups. **(The randomization was based on computer-generated random numbers.)**

[figure not shown]
Both groups received systemic steroid with/without intratympanic steroid. The experimental group receive additional oral topiramate for 6 weeks.

Follow-up time is 3 months.

This study is multi-center.

Location of the study is performed at Chang gung memorial hospital Linkou branch, Taipei branch, Taoyuan branch, and New Taipei Municipal Tucheng Hospital.

Flow Chart :

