4.3 Schedule of Activities

Time-Event scheme(評估時程表):

Phase	Screening	Treatment					Follow-up	
Day	0	0	7	14	21	28	56	84
Clinic visit	X	X	X	X	X	X	X	X
Screening/administration/safety								
ICF/assent form	X							
Inclusion/Exclusion criteria	X							
Medical and surgical history	X							
Lab exam	X							
MRI or ABR exam	X							
Randomization/Administration								
Randomization	X							
Administration of study drug	X	X	X	X	X	X		
Efficacy/Safety								
Symptoms			X	X	X	X	X	
Audiometry	X						X	X

The physician confirm that the patient meets the inclusion criteria at the initial visit (day 0). Then the patients would be asked if he/she is willing to participate into this clinical trial. If the patient agreed, then medical history taking, audiometry and lab examination, MRI or ABR examination will be arranged at same time. He/she will be randomized into either experimental arm or control arm. The treatment will be started immediately. The blood test will be performed at first visit and the data will be checked at day 7. Patients in both arms would follow up at our clinic at day 7,14,21,28,56, and 84. Pure tone audiometry and speech audiometry will be followed at day 56 and 84. Symptoms and adverse effects (safety monitoring) will be followed up at day 7,14,21,28, and 56.

5. Study Population

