9.1 Definitions and reports of Adverse Events

All adverse events that occur after the informed consent is signed (including run-in) must be recorded on the adverse event CRF (paper and/or electronic) whether or not related to study agent. AE Data Elements including:

- AE reported date
- AE Verbatim Term
- CTCAE Term (v 5.0)
- Event onset date and event ended date
- Severity grade
- Attribution to study agent (relatedness)
- Whether or not the event was reported as a Serious Adverse Event (SAE)
- Action taken with the study agent
- Outcome of the event
- Comments

Identify the adverse event using the NCI Common Terminology Criteria for Adverse Events (CTCAE) version 5.0. The CTCAE provides descriptive terminology and a grading scale for each adverse event listed.

AEs will be assessed according to the CTCAE grade associated with the AE term. AEs that do not have a corresponding CTCAE term will be assessed according to their impact on the participant's ability to perform daily activities as follows:

Grade	Severity	Description
1	Mild	
• Barely noticeable, does not influence functioning• Causing no limitations of usual activities
2	Moderate	
• Makes participant uncomfortable, influences functioning• Causing some limitations of usual activities
3	Severe	
• Severe discomfort, treatment needed• Severe and undesirable, causing inability to carry out usual activities
4	Life threatening	
• Immediate risk of death• Life threatening or disabling
5	Fatal	
• Causes death of the participant

The possibility that the adverse event is related to study drug will be classified as one of the following: not related, unlikely, possible, probable, definite.

DEFINITION of Serious Adverse Events: ICH Guideline E2A and GCP of Taiwan define serious adverse events as those events, occurring at any dose, which meet any of the following criteria:

- Results in death

- Is life threatening (Note: the term life-threatening refers to an event in which the patient was at risk of death at the time of the event; it does not refer to an event which hypothetically might have caused death if it were more severe).
- Requires inpatient hospitalization or prolongation of existing hospitalization
- Results in persistent or significant disability/incapacity
- Is a congenital abnormality/birth defect

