11.3 Analysis Population

All eligible participants will be included in the analyses. If the participant wishes to withdraw due to any reason after enrollment, the data will also be reported.

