11.4 Procedure for accounting for missing, unused and spurious data

The incomplete clinical data and sequencing data with poor quality will be excluded in the study.

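### Dosed patients who are later reclassified are removed from the study and from the analysed population, against the ticked ITT set and in tension with the adverse event rules

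*Protocol*

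**What the plan says.** **Order of events.** Section 4.3 describes one day-0 visit. After consent, "audiometry and lab examination, MRI or ABR examination will be arranged at same time", the patient is randomised, and "The treatment will be started immediately". On laboratory results it says: "The blood test will be performed at first visit and the data will be checked at day 7". No imaging, ABR or laboratory result is required before the first dose.

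**Later diagnosis.** Section 4.1: "Patients who were diagnosed as SSNHL but was later found to be other disease such as Meniere's disease, CP angle tumor will be excluded". The sentence goes on to make this an exclusion from the study, with no limit to efficacy.

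**Who is analysed.** Section 11.3: "All eligible participants will be included in the analyses". Its second sentence deals with voluntary withdrawal: "If the participant wishes to withdraw due to any reason after enrollment, the data will also be reported". Section 11.4 adds: "The incomplete clinical data and sequencing data with poor quality will be excluded in the study". The synopsis (Statistical Methods, item 3) ticks intention-to-treat as the efficacy set. Section 11.2.2 says that adverse effects are analysed at the end of the study, but not in whom.

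**Adverse events.** Section 9.1: "All adverse events that occur after the informed consent is signed (including run-in) must be recorded on the adverse event CRF", whether or not related to the study agent. Section 9.2 requires all adverse events to be followed and documented.

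**The concern.** The plan lets a patient be randomised and take topiramate before the tests that can overturn the diagnosis have been read. If another disease is then found, the stated rule is removal from the study. Two things are at stake.

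- **Efficacy comparison.** Removal after randomisation breaks the randomised comparison if it can differ by arm. The synopsis declares the trial open, so whoever reclassifies a patient knows the arm. Exclusion criterion 3 pairs Meniere's disease with fluctuating hearing loss, so that reclassification can rest on how hearing behaves after treatment starts, and hearing is the primary outcome. A tumour seen on imaging is far less open to this, because it does not depend on treatment.
- **Safety reporting.** A patient who has taken the drug has been exposed, whatever the later diagnosis. If such patients leave the scheduled visits and the analysed population, adverse event rates describe only those who stayed eligible.

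**Working it through.** **1. Can the exclusion fall after dosing?** The schedule table in section 4.3 puts MRI/ABR and randomisation in the screening column, but that column and the first treatment column are both day 0. The text arranges the tests and starts treatment at once. A result that arrives on a later day therefore arrives after the first dose. The same holds for hepatic insufficiency (exclusion criterion 8) if it first shows in blood results read at day 7; that patient would no longer be eligible in the sense of section 11.3.

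**2. Which rule covers such a patient?**

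| Section | Patients covered | Effect |
|---|---|---|
| 4.1 | Later found to have another disease | Out of the study, no limit stated |
| 5.3 | Withdrawn patients | Out of the audiology analysis only; reasons reported |
| 11.3, first sentence | Eligible participants | Included in the analyses, efficacy and safety not separated |
| 11.3, second sentence | Participants who wish to withdraw | Data also reported |
| 11.4 | Incomplete clinical data | Excluded, not limited to efficacy |
| Synopsis, missing data | Cases with missing data | Omitted, linked to efficacy |
| 9.1, 9.2 | Everyone after consent | Events recorded and followed |

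Voluntary withdrawals are protected by section 5.3 and by the second sentence of section 11.3. Patients removed on diagnosis are not: they meet section 4.1 and fail the word eligible in section 11.3. Sections 9.1 and 9.2 apply to them, but cover recording and following events. They do not say who is counted in the analysis, or that an excluded patient keeps the visits at which events are found.

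**3. The plan's own numbers.** Inputs from the synopsis: difference 7 dB (12 against 19), SD 13, two-sided alpha 0.05, 56 per group.

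- Noncentrality = 7 / (13 × √(2/56)) = 2.85 on 110 degrees of freedom. Power = 0.806, as stated; 55 per group gives 0.799, so 56 is the minimum.
- Enrolment: 112 / 0.8 = 140, so 70 per arm.
- Section 4.2: 140 − 28 = 112. The 10 screening failures must lie outside the 140, since 140 − 10 − 28 = 102. No separate allowance is made for patients excluded after randomisation.

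**4. Scale.** The protocol gives no reclassification rate. The shares x below are assumptions. The last two columns further assume that these exclusions come on top of the 20%: evaluable N = 112 × (1 − x), with the number per arm rounded down for the power.

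| x | Of 140 | Of 70 on topiramate | Evaluable N | Per arm | Power |
|---|---|---|---|---|---|
| 1% | 1.4 | 0.7 | 110.9 | 55 | 0.80 |
| 2% | 2.8 | 1.4 | 109.8 | 54 | 0.79 |
| 5% | 7 | 3.5 | 106.4 | 53 | 0.78 |
| 10% | 14 | 7 | 100.8 | 50 | 0.76 |

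If reclassified patients are meant to be part of the 28 drop-outs, power does not change. The loss of power is minor either way. The issue is who is removed, and on what knowledge.

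**The case against.** A reader might infer that exposed patients do drop out of safety follow-up and of the adverse event counts. The documents do not support that. Section 9.1 requires every event after consent to be recorded, section 9.2 requires all of them to be followed, and section 8 describes monitoring to the end of follow-up. No sentence takes safety visits away from an excluded patient.

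A reader might also put the planned drop-outs to use: 14 of 70 topiramate patients are incomplete; if 7 of them had intolerable effects, the rate is 7/70 = 10% among the exposed but 0/56 = 0% among those retained. This does not follow. Intolerable adverse effects are a named reason for withdrawal in section 5.3, which removes such patients from audiology only and reports their reasons, and section 11.3 reports their data. The 20% is an allowance for the audiometric sample size, not a count of patients left out of adverse event tables.

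Three further points have weight. Section 11.4 mentions sequencing data although the synopsis says that no specimens are collected, so it may be template text, and a recorded event is not incomplete merely because a later audiogram is missing. In section 4.1 the exclusion sentence stands before the randomisation sentence, and the flow chart is not shown, so exclusion before randomisation may have been meant. A safety set is commonly defined in an SAP, and none is shown.

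These limit the safety claim to a risk. They do not remove the point. The text of section 4.3 still puts dosing ahead of the results, section 4.1 is a stated rule and not a missing detail, and an SAP cannot recover safety visits that were never held.

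**Conclusion.** The point holds as a conflict between stated rules. Followed literally, sections 4.1, 4.3 and 11.3 remove randomised and dosed patients after an open-label reclassification that may depend on hearing after treatment. That contradicts the ticked intention-to-treat set. Set against sections 9.1 and 9.2, it leaves open whether these patients stay in safety follow-up and in the adverse event analysis, so they may be lost from both.

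The size is unknown: about 1 to 14 of 140 patients, roughly half on topiramate, if 1% to 10% are reclassified. Both the range and the even split between arms are assumptions. No bias in the adverse event rate can be calculated from the documents. The correction is worth making because it changes a stated rule at little cost, with medium confidence given that the flow chart and any SAP are not shown.

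**What to change.** Reconcile sections 4.1, 11.3 and 11.4 with sections 9.1 and 9.2 and with the ticked intention-to-treat set:

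- **Section 4.1:** flag a patient reclassified after randomisation as ineligible on review, instead of removing the patient from the study. Keep the patient in the same adverse event follow-up as all others.
- **Section 11.3:** define the safety set as everyone who received any study treatment, by treatment received, whatever their later eligibility. Reword the efficacy population so that it agrees with the synopsis.
- **Section 11.4:** state that it does not remove recorded adverse events.
- **Reporting:** give the number of reclassifications by arm, with the reason for each.
- **Length of safety monitoring:** the text of section 4.3 lists it to day 56, and section 8 extends it to 3 months. The two must be reconciled; this review does not choose between them.

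The cost is protocol wording and a few more patients kept on visits already scheduled. The stated adverse event rate may be slightly less favourable.

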- 2. Previous middle ear disorder such as chronic otitis media, or previous ear surgery
- 3. Meniere's disease and fluctuating hearing loss patients
- 4. Pregnancy or trying to become pregnant
- 5. Leukemia, hemodialysis, and patients who received chemotherapy before.
- 6. Previous head and neck radiotherapy
- 7. Cerebellopontine (CP) angle tumor such as vestibular schwannoma
- 8. Patients with moderate to severe hepatic insufficiency
- 9. Patients with major depression disorder or suicide attempt
- 10. Patients with glaucoma

Study Procedures :

1. Expected inclusion patient number (enrolled number: **140**; evaluable number: **112**)
The participants would be divided into two group, half in the experimental group and the other half in the control group.
2. All patients will receive audiology examination, laboratory examination, magnetic resonance imaging of brain or auditory brainstem response at the first visit. Then the patient would be followed at the clinic weekly till the sixth week. Audiology examination will be arranged during the first week and then monthly till 12 weeks.
3. As for the treatment, the control group will receive systemic steroid with/without intratympanic steroid for 2 weeks as the standard therapy for sudden sensorineural hearing loss. The experimental group will receive systemic steroid with/without intratympanic steroid for 2 weeks and simultaneously oral topiramate for 6 weeks.
4. There will be no specimen collection in this study.
5. The patients' gender, age, initial and final hearing threshold, laboratory examination result, audiology result and symptoms will be collected.

Concomitant Treatments : not applicable

1. Concomitant Therapy : Prescribe systemic steroid with/without intratympanic steroid
2. Prohibited Therapy : nil

Statistical Methods :

1. Main study Hypothesis : Equality Superiority Non-inferiority
 Equivalence Other _____
2. Estimated Sample Size : Anticipated enrolled size 140 , Estimated evaluable number 112
Anticipated enrolled size in our center 45 , Estimated evaluable number in our center 40

Protocol: The role of migraine prophylaxis agent topiramate in treating patients with migraine and sudden sensorineural hearing loss

Version: 6

Date: 20220812

PASS 15.0.13

2022/8/2 下午 02:01:50

Two-Sample T-Tests Assuming Equal Variance

Numeric Results for Two-Sample T-Test Assuming Equal Variance

Alternative Hypothesis: $H1: \delta = \mu_1 - \mu_2 \neq 0$

Target Power	Actual Power	N1	N2	N	μ_1	μ_2	δ	σ	Alpha

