4.2 Number of Patients

Enrolled number : **140**

Failed during screening : **10**

Drop-out number : **28**

Estimated evaluable number : **112** (experimental group 56, control group 56)

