5.2 Exclusion Criteria

Exclusion criteria:

- (1) Previous SSNHL history
- (2) Previous middle ear disorder such as chronic otitis media, or previous ear surgery
- (3) Meniere's disease and fluctuating hearing loss patients
- (4) Pregnancy or trying to become pregnant
- (5) Leukemia, hemodialysis, and patients who received chemotherapy before.
- (6) Previous head and neck radiotherapy
- (7) CP angle tumor such as vestibular schwannoma
- (8) Patients with moderate to severe hepatic insufficiency
- (9) Patients with major depression disorder or suicide attempt
- (10) Patients with glaucoma

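### Section 4.1's open-ended exclusion of patients re-diagnosed later allows an outcome-related removal after randomisation in an open trial, against the ticked intention-to-treat population

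*Protocol*

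**What the plan says.** Section 4.1 (Overall Design) states that a patient first diagnosed with sudden sensorineural hearing loss who "was later found to be other disease such as Meniere's disease, CP angle tumor will be excluded from this study". It gives no cut-off date, names no assessor and does not restrict the evidence to what was available at baseline.

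Section 4.3 (Schedule of Activities) describes the day-0 visit. After consent, "MRI or ABR examination will be arranged at same time" as history, audiometry and blood tests. Then: "He/she will be randomized into either experimental arm or control arm. The treatment will be started immediately". The schedule table puts MRI/ABR, randomisation and first study drug in the same day-0 screening column. The synopsis (Study Procedures) likewise places "magnetic resonance imaging of brain or auditory brainstem response at the first visit".

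Exclusion criterion (3) in section 5.2 reads "Meniere's disease and fluctuating hearing loss patients".

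The synopsis marks the trial as open, with the evaluator-blind box empty. It defines the primary endpoint as improvement rate and gain in pure tone audiometry from day 0 to day 84, and ticks intention-to-treat as the efficacy population. Section 11.3 instead analyses all participants who are eligible.

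**The concern.** A diagnosis that rests on how symptoms and hearing evolve cannot be made within one visit. If Meniere's disease is recognised after day 0, the patient has already been allocated and treated, and the evidence includes the course of hearing, which is what the primary endpoint measures. In an open trial the physician making the re-diagnosis knows the arm.

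Removing such patients means that membership of the analysis set depends partly on outcome and possibly on arm. The comparison is then no longer between the groups as randomised, and a difference in hearing gain can be created or hidden. The withdrawal rule in section 5.3 and the missing-data rules do not cover this: a re-diagnosed patient may have complete audiograms and may never have withdrawn. Nor is it a detail to leave to an analysis plan, because the protocol itself states the exclusion.

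**Working it through.** **Order of events**

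| Step | Source | Timing |
|---|---|---|
| Inclusion criteria confirmed, consent | Section 4.3 | Day 0 |
| MRI or ABR arranged | Section 4.3, synopsis | Day 0; time of reading not stated |
| Randomisation, treatment start | Section 4.3 | Day 0 |
| Blood test result checked | Section 4.3 | Day 7 |
| Symptom visits | Section 4.3 | Days 7, 14, 21, 28, 56 |
| Follow-up audiometry | Section 4.3 | Days 56, 84 |
| Exclusion for another disease found later | Section 4.1 | No limit |

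The two diagnoses named in section 4.1 behave differently.

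- **CP angle tumour.** It is present before day 0. If every patient has the same baseline test, removal on that result does not depend on arm or outcome. A residual risk remains because either MRI or ABR is enough, so a later MRI could be prompted by poor recovery.
- **Meniere's disease.** If it was not evident on day 0, it is recognised from the later course, which is after randomisation and related to the endpoint.

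**The plan's own figure.** Inputs from the PASS output in the synopsis: means 12 and 19 dB, difference 7, SD 13, two-sided alpha 0.05, 56 per arm.

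Noncentrality = 7 / (13 × √(2/56)) = 2.849. With 110 degrees of freedom the noncentral t gives power 0.806, which agrees with the stated 80.630%. Enrolment: 112 / 0.8 = 140.

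**Illustration of possible bias.** The documents give no removal rate, so what follows is assumed: no true effect, gain normal with mean 12 and SD 13 in both arms, 56 per arm, and removed patients drawn at random from those with gain below 5 dB.

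- z = (5 − 12)/13 = −0.538; density 0.345; lower-tail probability 0.295.
- Patients with gain below 5 dB lie on average 13 × 0.345/0.295 ≈ 15.2 dB below the arm mean.
- Removing 3 of 56 raises that arm's mean by 3 × 15.2 / 53 = 0.86 dB.
- Removing 1 of 56 raises it by 15.2 / 55 = 0.28 dB.

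Simulation (100,000 runs, two-sided 5% t-test):

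| Removed, arm A / arm B | Shift in difference | Rejection |
|---|---|---|
| 0 / 0 | 0.0 dB | 5.1% |
| 1 / 0 | 0.27 dB | 5.2% |
| 2 / 1 | 0.28 dB | 5.6% |
| 3 / 0 | 0.87 dB | 7.0% |
| 3 / 3 | 0.0 dB | 6.0% |

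The 3 / 3 row shows no shift; rejection rises slightly because trimming the lower tail shrinks the observed SD (to about 12.7).

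The result depends on who is removed. For 3 removed from one arm only, drawing them from the lower half of that arm gives 0.59 dB and 5.4%. Taking the three worst recoverers, an extreme case, gives 1.46 dB and 10.4%.

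**The case against.** The strongest reply is that section 4.1 describes screening. The exclusion sentence comes before the sentence on randomisation, MRI/ABR stands in the screening column, section 4.2 expects screening failures, and the flow chart that might settle the order is not reproduced. This stands in part. Some exclusions, particularly those based on imaging, may well precede randomisation. It does not cover a diagnosis drawn from the clinical course, which one visit cannot supply.

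Three stronger readings are tempting, and the documents do not support them.

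- **That MRI/ABR is unread when patients are randomised.** The wording makes this plausible, but no section says when the result is read.
- **That fluctuation could be seen only in the day-56 and day-84 audiograms.** Section 4.3 also has symptom visits from day 7 to day 28, and the synopsis mentions audiology in the first week and then monthly. Section 4.1 also does not say that criterion (3) is re-applied to follow-up audiograms.
- **That the 10 patients listed as "Failed during screening" in section 4.2 come off the evaluable number, leaving 102.** The count closes without them (140 − 28 = 112), so they are most naturally outside the 140. Nothing shows that later exclusions are not already among the 28 drop-outs.

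It is also fair to say that settling the analysis population, now intention-to-treat in the synopsis but all eligible participants in section 11.3, would resolve much of this. The section 4.1 sentence would still need rewording, because it is what makes a randomised patient ineligible afterwards.

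**Conclusion.** The point holds in a limited form. As written, section 4.1 permits randomised patients to be removed during follow-up for a reason related to the outcome, with the arm known, and this conflicts with the ticked intention-to-treat population. It applies mainly to Meniere's disease or similar re-diagnoses during follow-up, and only weakly to a CP angle tumour shown by the baseline test.

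The documents fix neither the size nor the direction of any bias. The 0.86 dB shift and 7% rejection rate describe one assumed case, three low-gain patients removed from one arm and none from the other. They should not be read as a forecast, and removing one patient or similar numbers from both arms has less effect. The issue is selection rather than lost precision. It should be fixed; confidence is medium, because the order of imaging and randomisation is partly inferred.

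**What to change.** In section 4.1, allow removal from the analysis after randomisation only for a condition that was present before day 0 and is shown by the day-0 MRI or ABR. Apply the rule identically in both arms and without reference to follow-up audiograms.

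Keep patients re-diagnosed during follow-up, for example with Meniere's disease, in the primary analysis as randomised. Repeat the analysis without them as a sensitivity analysis, and report the number re-diagnosed in each arm. Align section 11.3 with the same rule. This concerns the analysis set only; how a re-diagnosed patient is treated is a separate clinical matter.

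The cost is a few sentences and one extra analysis. A small number of patients with another cause of hearing loss will stay in the primary comparison and may slightly dilute the effect.
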